Appendix 6: Schedule of Assessments

Study Plan – Part A (Single Dose)

	Pre-screening ^d	Screening	Day -2	Day -1	Days 1 to 3	Day 4	Day 7 (± 2 days)	Day 10 (± 2 days)	Day 14 (± 2 days)	Poststudy (Day 28 ± 2 days)
Inclusion/exclusion criteria		X								
Demographic data		X								
Medical history		X								
Urine drugs of abuse screen		X	X							
Alcohol breath test		X	X							
Cotinine test		X	X							
Serology		X								
Hormone panel		X								
Urine pregnancy test ^a		X	X							X
Informed consent	X	X								
Study residency:										
Check-in			X							
Check-out					Day 3 (48 hours postdose)					
Non-residential visit	X	X				X	X	X	X	X
Study drug administration:					Day 1 (0 hours)					
Safety and tolerability:										
Adverse event recording		X	X	X	Ongoing	X	X	X	X	X
Concomitant medication recording		X	X	X	Ongoing	X	X	X	X	X
Supine blood pressure, pulse rate, respiratory rate, and body temperature		X			Predose, 1, 2, 4, 8, 24 (± 1 hour), and 48 hours postdose	X	X	X	X	X

	Pre-screening ^d	Screening	Day -2	Day -1	Days 1 to 3	Day 4	Day 7 (± 2 days)	Day 10 (± 2 days)	Day 14 (± 2 days)	Poststudy (Day 28 ± 2 days)
Supine 12-lead ECG		X			Predose, 4, 24 (± 1 hour) and 48 hours postdose		X		X	X
Continuous ECG extraction ^{b,c}				-24, -23.5, -23, -22.5, -22, -21.5, -21, -20, -18, -16, -12 hours	Day 1: Predose, 0.5, 1, 1.5, 2, 2.5, 3, 4, 6, 8, 12 and 24 hours					
Heat pain threshold test (heat pain threshold and heat pain tolerance)					Day 1: predose, 2, 4, 12, and 24 hours postdose (± 1 hour)					
Clinical chemistry, haematology, and urinalysis		X	X		48 hours postdose		X		X	X
Height and BMI		X								
Body weight		X	X							X
Physical examination		X								
Symptom-directed physical examination					Prior to discharge		X		X	X

	Pre-screening ^d	Screening	Day -2	Day -1	Days 1 to 3	Day 4	Day 7 (± 2 days)	Day 10 (± 2 days)	Day 14 (± 2 days)	Poststudy (Day 28 ± 2 days)
Injection site assessment					Predose, 1, 2, 4, 8, 24, 48 hours postdose		X		X	X
Pharmacokinetics^e										
Blood sampling					Predose, 0.5, 1, 1.5, 2, 3, 4, 6, 8, 12, 16, 24, 36 and 48 hours postdose	X	X	X	X	X
Pharmacodynamics^d:										
Intradermal capsaicin test (capsaicin-evoked pain and secondary hyperalgesia measurement)	X		X		Day 2 (The area of secondary area of hyperalgesia will be evaluated at 5 and 30 minutes post-capsaicin injection)					

Abbreviations: BMI = body mass index; ECG = electrocardiogram.

^a A positive urine pregnancy test result will be confirmed with a serum pregnancy test.

^b All times are relative to dosing with OLP-1002.

^c Continuous ECG recording may begin at approximately 25 hours before dosing to allow for checks to be completed prior to the first extraction timepoint and will continue for 24 hours postdose, ie, until after the last timepoint for ECG extraction (24 hours postdose). At timepoints for ECG extractions, subjects will be supinely resting for a total of 15 minutes (10-minute supine rest period, 5-minute extraction). Data will be archived for potential future analysis and will not be available for review during the study.

^d Pharmacodynamic assessment groups only.

^e PK analysis in Part A will initially only be conducted for groups receiving $\geq 12 \mu\text{g}$ OLP-1002, with retrospective analyses of samples from lower dose groups occurring in the event of PK data being quantifiable at doses $\geq 12 \mu\text{g}$ and if supported by bioanalytical stability data.

Study Plan – Part B (Multiple Dose)

	Screening	Day -1	Days 1-15	Day 18 (± 2 days)	Day 22 (± 2 days)	Day 25 (± 2 days)	Day 29 (± 2 days)	Poststudy (Day 57 ± 2 days)
Inclusion/exclusion criteria	X							
Demographic data	X							
Medical history	X							
Urine drugs of abuse screen	X	X						
Alcohol breath test	X	X						
Cotinine test	X	X						
Serology	X							
Hormone panel	X							
Urine pregnancy test ^a	X	X			X		X	X
Informed consent	X							
Study residency:								
Check-in		X						
Check-out			Day 15 (48 hours postdose)					
Non-residential visit	X			X	X	X	X	X
Study drug administration:			Days 1, 4, 7, 10, and 13					
Safety and tolerability:								
Adverse event recording	X	X	Ongoing	X	X	X	X	X
Concomitant medication recording	X	X	Ongoing	X	X	X	X	X
Supine blood pressure, pulse rate, respiratory rate, and body temperature	X		Day 1: predose, 1, 2, 4 and 8 hours postdose Day 2, Day 4 (postdose), Day 5, Day 7 (postdose), Day 9, Day 10 (postdose), Day 12, Day 13: predose, 1, 2, 4 and 8 hours postdose, and Day 15	X	X	X	X	X

	Screening	Day -1	Days 1-15	Day 18	Day 22	Day 25	Day 29	Poststudy (Day 57 ± 2 days)
Heat pain threshold test (heat pain threshold and heat pain tolerance)	X		Day 1 and Day 13: predose, 1, 2, 4, 8, 24 hours postdose					
Supine 12-lead ECG	X		Day 1: predose and 4 hours postdose Day 4: predose and 4 hours postdose Day 7: predose and 4 hours postdose Day 10: predose and 4 hours postdose Day 13: predose and 4 hours postdose Day 15		X		X	X
Clinical chemistry, haematology, and urinalysis	X	X	Days 2, 5, 9, 12, 17		X		X	X
Height and BMI	X							
Body weight	X	X						X
Physical examination	X							
Symptom-directed physical examination			Days 1, 4, 7, 10, 13		X		X	X
Injection site assessment			Day 1: predose and 4 hours postdose Day 4: predose and 4 hours postdose Day 7: predose and 4 hours postdose Day 10: predose and 4 hours postdose Day 13: predose and 4 hours postdose Day 15		X		X	X
Pharmacokinetics:								
Blood sampling ^b			Day 1 and Day 13: Pre dose, 0.5, 1, 1.5, 2, 3, 4, 6, 8 and 12 hours post dose Days 4, 7, 10 Predose Day 15	X	X	X	X	X

Abbreviations: BMI = body mass index; ECG = electrocardiogram.

^a Positive urine pregnancy test results will be confirmed with a serum pregnancy test.

^b PK timepoints will be reviewed based on emerging data and may be updated.

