7.3.4.2. Continuous (24-hour) Electrocardiogram

At the times indicated in the Schedule of Assessments ([Appendix 6](#)), continuous (24-hour) ECGs will be performed.

Subjects will be supine for at least 10 minutes before the extraction timepoint and for 5 minutes from the start of each extraction timepoint. Each extraction will last for 5 minutes. Environmental distractions (eg, television, playing games, radio, conversation) should be avoided during the pre-ECG time window.

Continuous 24-hour ECGs are not planned for Part B of the study but may be implemented if any clinically significant findings are identified in the data from Part A.

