1.5. Summary of Nonclinical Pharmacokinetics

In rats, following a single SC dose of ^{14}C -OLP-1002, the time of maximum observed concentration (T_{\max}) was 0.5 to 1 hour for both radioactivity and parent compound. Plasma concentrations of total radioactivity were quantifiable through the last sampling time of 72 hours postdose, but was variable for the parent compound. The elimination half-life ($t_{1/2}$) of total radioactivity from plasma was 23 hours. Total radioactivity distributed into tissues, including those of the CNS protected by the blood-brain barrier. ^{14}C -OLP-1002-derived total radioactivity was not rapidly excreted from rats, with minimal amounts present in urine and feces. The bulk of the total radioactivity remained in carcasses, primarily in kidneys (cortex and medulla) and liver. Parent ^{14}C -OLP-1002 was present in plasma and tissues, but concentrations declined over time and were substantially lower than total radioactivity concentrations at the later sampling times.

After a single SC administration of ^{14}C -OLP-1002 to rats, the highest concentrations of total radioactivity were retained predominantly in the liver (10.4% to 13.3% of the dose), kidney cortex (3.47% to 4.96%), and kidney medulla (1.10% to 1.59% of the dose) through 168 hours postdose. For all other tissues, the total amounts of total radioactivity were substantially less, ranging from 0.0000203% in the 5th DRG to 0.327% in the spleen. Radioactivity was excreted slowly via both the renal and fecal routes of elimination. Total average recoveries of radioactivity in urine and feces through 336 hours postdose accounted for 2.31% and 1.75% of the administered radioactivity, respectively. The bulk of the administered total radioactivity was retained in the rat carcasses through 168, 336, 504, and 840 hours postdose. The kidney cortex, kidney medulla, and liver were the 3 tissues that retained the greatest amounts of the administered radioactivity.

Following a 16.1- $\mu\text{g}/\text{kg}$ dose in rats, the plasma concentrations were still quantifiable at 72 hours postdose and the rate of elimination was slow, with $t_{1/2}$ 17.5 hours. It was not possible to accurately define the elimination phase for the 2.67- and 5.28- $\mu\text{g}/\text{kg}$ dose levels.

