In cynomolgus monkeys, following a single SC dose of ^{14}C -OLP-1002, T_{\max} ranged from 0.25 to 1 hour for both total radioactivity and parent compound. Concentrations of total radioactivity were sustained in blood and plasma through the last sampling time of 144 hours postdose. Concentrations of parent compound were sustained in plasma through the last sampling time of 144 hours postdose in 2 of 3 monkeys, and were similar to plasma total radioactivity concentrations at 8 hours postdose. From 24 to 144 hours postdose, plasma concentrations of total radioactivity were substantially higher than for parent ^{14}C -OLP-1002 plasma concentrations.

The mean C_{\max} of parent ^{14}C -OLP-1002 in plasma was 1.96 ng/mL. The mean plasma T_{\max} was 0.833 hours. Plasma exposure of parent ^{14}C -OLP-1002 based on AUC extrapolated to infinity ($\text{AUC}_{0-\infty}$), was 12.7 ng·h/mL. After reaching C_{\max} , plasma concentrations of parent ^{14}C -OLP-1002 declined with a mean $t_{1/2}$ of 84 hours.

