2. OBJECTIVES AND ENDPOINTS

2.1. Objectives

The primary objective of the study is to assess the safety and tolerability of single and multiple SC doses of OLP-1002 in healthy subjects.

The exploratory objectives of the study are to evaluate the PD effect of OLP-1002 following single SC doses in healthy volunteers using a capsaicin pain model, and to monitor the effects of single SC doses of OLP-1002 on cardiac QT interval. Where possible, single and/or multiple subcutaneous dose pharmacokinetics of OLP-1002 in healthy subjects will be determined.

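### The QTcF stopping and withdrawal rules have no scheduled, reviewable ECG near the expected plasma peak: 12-lead readings start 4 h after dosing, and the Part A recordings that cover the peak cannot be reviewed during the study

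*Protocol*

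**What the plan says.** **Rules that use QTcF.** Section 3.7 stops escalation, in both parts, when 2 or more subjects in a group have a QTcF rise above 60 msec and/or a value above 500 msec. Section 4.4 uses the same limits to withdraw a subject.

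**ECGs that can feed those rules.** Appendix 6 schedules the Part A 12-lead ECG at "Predose, 4, 24 (± 1 hour) and 48 hours postdose", then on Days 7, 14 and 28. The Part B row begins "Day 1: predose and 4 hours postdose Day 4: predose and 4 hours postdose" and keeps that pattern on Days 7 and 10 and through "Day 13: predose and 4 hours postdose". Days 15, 22, 29 and 57 follow.

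**Continuous ECG.** Part A has Day 1 extractions at 0.5, 1, 1.5, 2, 2.5 and 3 h and later. Footnote c states: "Data will be archived for potential future analysis and will not be available for review during the study". Section 7.3.4.2 does not plan continuous ECG for Part B, but says it "may be implemented if any clinically significant findings are identified in the data from Part A".

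**Expected peak.** Section 1.5 reports that Tmax in monkeys "ranged from 0.25 to 1 hour for both total radioactivity and parent compound", with a mean of 0.833 h. In rats it "was 0.5 to 1 hour for both radioactivity and parent compound". Section 3.5.2 predicts human exposure from the monkey.

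**QT objective.** Section 2.1 lists, as exploratory, "to monitor the effects of single SC doses of OLP-1002 on cardiac QT interval". Section 2.2.2 ties this to the archived continuous recording.

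Sections 1 and 2 are available only in the version 2.1 text. The Amendment 3 summary lists changes to Appendix 3 and Appendix 6 only, so I take Sections 1 and 2 as current.

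**The concern.** A stopping rule can act only on data that are collected and read in time. For QTcF, the scheduled readings in both parts begin hours after the expected peak. The readings that span the peak are set aside until after the study. A QTc effect that tracks plasma concentration and fades by 4 h would not reach the escalation meeting on the scheduled data, and would not trigger withdrawal of the subject.

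The same gap reaches the Part B provision. Section 7.3.4.2 makes continuous ECG in Part B depend on findings in Part A data, yet the Part A data most able to show an early effect cannot be consulted when that decision is taken.

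Part B is where this counts most. Section 3.5.3 allows exposure there up to about 2-fold the Part A maximum.

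The other cardiovascular rules in Section 3.7 are better served. The tachycardia and hypertension criteria can draw on supine vital signs at 1 and 2 h, on Day 1 in Part A and on Days 1 and 13 in Part B.

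**Working it through.** **1. Schedule against expected peak.**

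| Measurement | Scheduled postdose times before 4 h | Reviewable in the study? |
|---|---|---|
| 12-lead ECG, Part A | none | yes |
| 12-lead ECG, Part B dosing days | none | yes |
| Continuous ECG, Part A | 0.5, 1, 1.5, 2, 2.5, 3 h | no (footnote c) |
| Vital signs, Part A Day 1; Part B Days 1 and 13 | 1, 2 h | yes |

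The first reviewable postdose ECG comes 4 − 1 = 3 h to 4 − 0.25 = 3.75 h after the animal Tmax range. Relative to the monkey mean the lag is 4 − 0.833 = 3.167 h.

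**2. Is 4 h still close to peak because the half-life is long?** Inputs are the monkey values in Sections 1.5 and 3.5.2: Cmax 1.96 ng/mL, AUC0-∞ 12.7 ng·h/mL, half-life 84 h.

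- A single-phase fall from Cmax at 84 h would give AUC = 1.96 × 84 / ln 2 ≈ 238 ng·h/mL, against the stated 12.7. The 84 h phase cannot describe the fall from the peak.
- Even if all the AUC were terminal, that phase would start at 12.7 × ln 2 / 84 = 0.105 ng/mL, and 0.105 / 1.96 ≈ 5% of Cmax. Most of the peak is lost in a faster phase.

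**3. Concentration at 4 h.** As a simplification, treat the whole AUC as lying after the peak.

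- One effective phase: exp(−3.167 / (12.7 / 1.96)) = exp(−3.167 / 6.48) = 0.61.
- Two phases, with an assumed share f of AUC in the 84 h phase. Let B = f × 12.7 × ln 2 / 84, A = 1.96 − B and k = A / ((1 − f) × 12.7). Then C(t)/Cmax = [A·exp(−k(t − 0.833)) + B·exp(−(ln 2 / 84)(t − 0.833))] / 1.96.
- Example, f = 0.5: B = 0.0524, A = 1.9076, k = 0.300. At 4 h this gives (1.9076 × 0.386 + 0.0524 × 0.974) / 1.96 = 0.40.

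| Terminal share f | C(1 h)/Cmax | C(4 h)/Cmax |
|---|---|---|
| one effective phase | 97% | 61% |
| 0.10 | 97% | 58% |
| 0.25 | 97% | 53% |
| 0.50 | 95% | 40% |
| 0.75 | 91% | 19% |
| 0.90 | 79% | 6% |

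The document does not give f, so the 4 h value can only be bracketed, at about 6 to 61% of Cmax. Every case lies below peak, and every case puts 1 h much closer to it.

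**4. Part B exposure.** Half the top Part A dose with the predicted 3.7-fold accumulation gives 0.5 × 3.7 = 1.85, which matches the protocol's figure of about 2-fold. With the protocol's own accumulation factor for Cmax, 2.28, it is 0.5 × 2.28 = 1.14. The peak itself is therefore predicted to rise less than overall exposure.

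**The case against.** **The QT objective.** A reader might infer that the QT objective itself misses the peak. The documents do not support that. The objective is exploratory, covers single doses only, and has as its endpoint the continuous recording, which includes extractions at 0.5 and 1 h. Continuous ECG in Part B has no bearing on it. Archiving is also a disclosed choice: Section 3.4 links it to a possible thorough QT waiver.

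**No peak ECG possible at all.** This would also go too far. Section 7.3.4.1 allows unscheduled 12-lead ECGs, Section 7.3 allows timepoints to be adjusted, and continuous ECG in Part B is conditional rather than ruled out. The Section 7.3.4.2 trigger is not empty, since 12-lead findings could meet it. None of these provisions obliges a reading near the peak.

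**Low prior risk.** This is the strongest point. Section 1.3 reports no hERG inhibition at 2 µM and no significant toxic cardiovascular effect in monkeys up to 100 nmol/kg. Since 100 nmol corresponds to 462.29 µg, the molecular weight is about 4,623. The predicted Cmax at 20 µg, 0.129 ng/mL, is then 0.129 / 4,623 × 1,000 ≈ 0.028 nM, and 2,000 / 0.028 is roughly 70,000-fold below the hERG concentration tested. The drug acts on splicing; one animal study showed onset at 4 days, and another measured protein reduction one day after dosing. Readings at 24 and 48 h and later suit an effect of that kind.

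**Animal Tmax.** The 0.25 to 1 h range is not a human figure, and human absorption could be slower.

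All of this stands and lowers the likelihood of harm. It does not give the QTcF rules a scheduled reading near the peak that the protocol's own data lead one to expect.

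**Conclusion.** The point holds for the QTcF stopping and withdrawal rules. In both parts, no scheduled ECG that can be reviewed during the study falls before 4 h, against an animal Tmax of 0.25 to 1 h. The concentration at 4 h is below peak by an amount the document cannot fix: about 6 to 61% of Cmax as the assumed terminal share of AUC varies. This rests on the monkey profile carrying over to humans, as Section 3.5.2 assumes for exposure.

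The recordings that would close the gap cannot inform escalation or the Part B trigger. Data capture for the exploratory QT objective is sound, and the nonclinical cardiac data and slow mechanism make an acute effect less likely. The right label is a cheap improvement to safety monitoring, not a defect that undermines the trial.

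**What to change.** Reconcile the 12-lead schedule, footnote c, the Section 7.3.4.2 trigger and Section 3.7:

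- Add a single 12-lead ECG at the 1 h supine vital-signs time already in Appendix 6: Part A Day 1, and Part B Days 1 and 13.
- Include that reading in the data reviewed before each escalation (Section 3.6).
- State in Section 7.3.4.2 that the trigger for continuous ECG in Part B refers to the 12-lead ECGs reviewed during the study.

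Leave the QT objective, its continuous-ECG endpoint and all stopping and withdrawal thresholds unchanged. Recasting the objective as 12-lead QTcF would discard its only data source that covers the peak.

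The cost is one extra resting ECG per subject in Part A and two in Part B, when the subject is already supine, plus a short schedule and wording amendment. Part B Days 4, 7 and 10 would still have no early ECG. Days 1 and 13 bracket the first and last doses, which keeps the burden small.

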4.4. Subject Withdrawal and Replacement

A subject is free to withdraw from the study at any time. In addition, a subject will be withdrawn if any of the following criteria are met:

- noncompliance with the study restrictions that might affect subject safety or study assessments/objectives, as considered applicable by the Investigator (or designee)
- any clinically relevant sign or symptom that, in the opinion of the Investigator (or designee), warrants subject withdrawal, including:
 - a serious adverse reaction (i.e., a SAE considered at least possibly related to OLP-1002 administration),
 - severe non-serious adverse reaction (i.e., severe non-serious AE considered to at least possibly related to OLP-1002 administration),
 - elevated AST, ALT, ALK (3 x ULN) or total bilirubin (2 x ULN),
 - QTcF increases > 60 msec compared to baseline (predose for Part A or Day 1 predose for Part B) and/or absolute QTcF values > 500 msec (confirmed by repeat measurement),
 - Tachycardia (> 150 beats/min) in the resting supine position (confirmed by 2 repeat measurements),
 - Severe hypertension (systolic blood pressure > 180 mmHg and/or diastolic blood pressure > 110 mmHg) in the resting supine position (confirmed by 2 repeat measurements).

If a subject is withdrawn, the Sponsor will be notified and the date and reason(s) for the withdrawal will be documented in the subject's electronic Case Report Form (eCRF). If a subject is withdrawn, efforts will be made to perform all follow-up assessments, if possible ([Appendix 6](#)). Other procedures may be performed at the Investigator's (or designee's) and/or Sponsor's discretion. If the subject is in-house, these procedures should be performed before the subject is discharged from the clinic. The Investigator (or designee) may also request that the subject return for an additional Follow-up visit. All withdrawn subjects will be followed until resolution of all their AEs or until the unresolved AEs are judged by the Investigator (or designee) to have stabilized.

Subjects who are withdrawn for reasons not related to study drug may be replaced following discussion between the Investigator and the Sponsor. Subjects withdrawn as a result of AEs thought to be related to the study drug will generally not be replaced.

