7.3.3. Vital Signs

Supine blood pressure, supine pulse rate, respiratory rate, and body temperature will be assessed at the times indicated in the Schedule of Assessments in [Appendix 6](#). Vital signs may also be performed at other times if judged to be clinically appropriate or if the ongoing review of the data suggests a more detailed assessment of vital signs is required.

Day 1 predose blood pressure, pulse rate, and respiratory rate will be measured in triplicate at approximately 2-minute intervals. The median value will be used as the baseline value in the data analysis. All subsequent measurements will be performed singly and repeated once if outside the relevant clinical reference ranges.

Subjects must be supine for at least 5 minutes before blood pressure, pulse rate, and respiratory rate measurements.

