7.3.4. Electrocardiogram

7.3.4.1. 12-lead Electrocardiogram

Resting 12-lead ECGs will be recorded after the subject has been supine and at rest for at least 5 minutes at the times indicated in the Schedule of Assessments in [Appendix 6](#). Single 12-lead ECGs will be repeated once if either of the following criteria apply:

- QTcF value > 500 msec
- QTcF change from the mean baseline (Day 1 predose) is > 60 msec.

Additional 12-lead ECGs may be performed at other times if judged to be clinically appropriate or if the ongoing review of the data suggests a more detailed assessment of ECGs is required. The Investigator (or designee) will perform a clinical assessment of each 12-lead ECG.

Day 1 predose 12-lead ECGs will be measured in triplicate at approximately 2-minute intervals. The mean value will be used as the baseline value in the data analysis. All subsequent measurements will be performed singly and repeated once if outside the relevant clinical reference ranges.

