3.1.2. Part B

Part B will comprise a multiple-dose, sequential-group study. Overall, 24 subjects will be studied in 3 groups (Groups B1 to B3), with each group consisting of 8 subjects. Up to 3 additional groups (24 subjects in total) may be included for further assessment of safety and tolerability ([Section 3.3](#)).

Potential subjects will be screened to assess their eligibility to enter the study within 28 days prior to the first dose administration. Each subject will participate in 1 treatment period only and reside at the CRU from Day -1 until Day 15.

All subjects will return for non-residential visits on Days 18 (± 2 days), 22 (± 2 days), 25 (± 2 days), and 29 (± 2 days), and for a poststudy visit on Day 57 (± 2 days).

[figure not shown]
In each of Groups B1 to B3, 6 subjects will receive OLP-1002 and 2 subjects will receive placebo. For all subjects, a single subcutaneous dose will be administered on Days 1, 4, 7, 10, and 13. Prior to each dosing occasion a physician will review the available safety and tolerability data from each subject to confirm it is acceptable to continue dosing. The dosing frequency in Part B may be changed following review of data from groups in Part A ([Section 3.4](#)).

Sentinel dosing will only occur in Part B at dose levels where exposure to OLP-1002 at steady state is predicted to exceed exposures that have been shown to be safe and well tolerated in earlier groups in Parts A or B. In the event of sentinel dosing, 2 subjects (1 active, 1 placebo) will be dosed at least 4 days prior to the remaining 6 subjects (5 active: 1 placebo). Safety data for the sentinel subjects from at least 2 additional doses will be reviewed prior to dosing the remaining subjects (i.e. sentinel subjects' safety data after doses 1 and 2 will be reviewed prior to the remaining subjects receiving dose 1). In addition, safety data from each subject will be reviewed by a physician prior to each dose to approve continued dosing.

Doses will be administered in an escalating manner following satisfactory review of safety, tolerability, and PK data up to Day 22 (216 hours post-final dose) from the lower dose levels. Part B may start after a review of the safety, tolerability, and available PK for Groups A1 to A6. The total daily dose administered will not exceed the highest single dose given in Part A.

An overview of the study design is shown in [Figure 2](#).

Figure 2: Study Schematic (Part B)

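### Part B schedules no predose blood pressure on Days 4, 7 and 10, so before doses 2, 3 and 4 the latest scheduled reading is nominally 48, 48 and 24 h old

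*Protocol*

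**What the plan says.** Part B gives five doses, on Days 1, 4, 7, 10 and 13, to subjects who stay in the unit from Day -1 to Day 15 (Section 3.1.2 and Appendix 6). In the Part B vital-signs row of Appendix 6, Day 1 has a predose reading and readings at 1, 2, 4 and 8 h. The row continues "Day 2, Day 4 (postdose), Day 5, Day 7 (postdose), Day 9, Day 10 (postdose), Day 12, Day 13: predose", with the same four postdose hours on Day 13 and a last in-house reading on Day 15. Predose blood pressure therefore appears on two of the five dosing days.

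Section 3.1.2 states: "Prior to each dosing occasion a physician will review the available safety and tolerability data from each subject". It is read here from the version 2.1 text, and the Amendment 3 summary lists no change to it. Section 4.4 lists among the withdrawal criteria for an individual subject: "Severe hypertension (systolic blood pressure > 180 mmHg and/or diastolic blood pressure > 110 mmHg) in the resting supine position", confirmed by two repeat measurements. Section 3.7 stops dose escalation for the same finding in one subject.

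Other procedures are scheduled before dosing on the three days in question. The ECG row reads "Day 4: predose and 4 hours postdose Day 7: predose and 4 hours postdose Day 10: predose and 4 hours postdose", the injection-site row has the same timing, and the PK row includes "Days 4, 7, 10 Predose". A symptom-directed physical examination falls on the same days, with no time given relative to dosing.

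**The concern.** The review before each dose is where a subject who meets a withdrawal criterion should be caught. On Days 4, 7 and 10 the scheduled predose ECG lets the physician check QTcF and heart rate against Section 4.4. No measurement listed as predose on those days gives a blood pressure. If pressure has passed the limit since the last reading, the next scheduled reading comes after the dose has been given, unless someone asks for one sooner.

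These are also doses over which exposure is expected to build. Section 3.4.1 works with a predicted half-life of 180 h and assumes 4-fold accumulation if exposure cannot be quantified, while doses are 72 h apart.

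The row looks carried over rather than chosen. It is identical in version 1 of the protocol, which had neither the review before each dose nor the hypertension withdrawal criterion. Amendment 1 added both and left the row as it was. No reason for omitting predose blood pressure is given in the text shown, and Day 13 includes it.

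**Working it through.** The protocol gives no figure to reproduce; the check is day arithmetic on the Part B schedule.

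**Inputs.** Dosing days 1, 4, 7, 10 and 13 (72 h apart). Blood pressure on Days 1, 2, 4, 5, 7, 9, 10, 12, 13 and 15, predose on Days 1 and 13 only, and postdose only on Days 4, 7 and 10 (Appendix 6). Three groups of 6 active and 2 placebo subjects (Section 3.1.2).

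**Age of the latest scheduled reading at the review.** Nominal age = 24 h × (dosing day − last earlier day with a reading); 0 where a predose reading is scheduled. A set is one scheduled round of vital signs; entries without stated hours are counted as one set.

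| Dose | Day | Last scheduled reading | Nominal age | Sets since previous dose |
|---|---|---|---|---|
| 2 | 4 | Day 2 | 24 × (4 − 2) = 48 h | Day 1 at 1, 2, 4, 8 h + Day 2 = 5 |
| 3 | 7 | Day 5 | 24 × (7 − 5) = 48 h | Day 4 postdose + Day 5 = 2 |
| 4 | 10 | Day 9 | 24 × (10 − 9) = 24 h | Day 7 postdose + Day 9 = 2 |
| 5 | 13 | Day 13 predose | 0 h | Day 10 postdose + Day 12 + Day 13 predose = 3 |

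**Clock times.** Days 2, 5 and 9 carry none. If the reading falls between the dosing hour and 12 h later, the ages are 36–48, 36–48 and 12–24 h. If dosing is at 08:00–10:00 and readings are at 08:00–20:00, they are 36–50, 36–50 and 12–26 h. Under either assumption none of the three doses has a scheduled reading from the same day before dosing.

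**Dosings affected.** 3 doses × 24 subjects = 72; active 3 × 18 = 54; placebo 3 × 6 = 18.

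**Sets on Days 1–15.** Day 1: 5. Days 2, 4, 5, 7, 9, 10 and 12: 7. Day 13: 5. Day 15: 1. Total 5 + 7 + 5 + 1 = 18. Three predose sets make 21, and the nominal ages before doses 2, 3 and 4 fall to about 0 h.

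**The case against.** The strongest reply is that nothing here is contradicted. The review covers available data, and Section 7.3.3 says: "Vital signs may also be performed at other times if judged to be clinically appropriate". Section 7.3 lets timepoints be adjusted, subjects are resident, and they are asked about symptoms at least daily. A physician who doubts the last reading can take another at once. All of this is true, and it is why the point is minor. It does not put a reading in the schedule: a discretionary measurement depends on someone seeing a reason to ask.

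Second, the schedule has a pattern. The vital signs on Days 2, 5, 9 and 12 coincide with the safety laboratory samples, so the liver values behind other withdrawal criteria are also one or two days old at the review. That is fair, but a laboratory result needs a blood sample and processing, whereas blood pressure can be read at the bedside just before the dose.

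Third, 48 h is only about 0.27 of the predicted half-life (48/180), and monkey plasma levels peaked within 1 h (Section 1.5). For an effect driven by plasma level, postdose readings are the informative ones, and every dosing day has at least one. This stands for such effects; it does not exclude a delayed one.

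Fourth, the harm is hypothetical. Section 1.3 reports no significant toxic effect on cardiovascular function in monkeys, and the 72 dosings count administrations, not risk. Both remarks are right. It is also unknown whether the symptom-directed examination precedes dosing or includes blood pressure.

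**Conclusion.** The gap is real and small. Before doses 2, 3 and 4, three of the four repeat doses, the latest scheduled blood pressure is nominally 48, 48 and 24 h old, and a listed withdrawal criterion has no measurement scheduled that day before the dose. The physician is not without data, since at least two scheduled sets follow each previous dose and any confirmed reading counts. No blood-pressure signal is known, so the case rests on precaution in first-in-human repeat dosing with predicted accumulation.

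The figures assume the printed day grid. Section 3.1.2 allows the dosing frequency to change after Part A, and Section 3.5.3 leaves frequency and duration to be decided. The hours depend on clock times that the schedule does not give. The point is worth considering as an inexpensive improvement, not as an error that affects the study's conclusions.

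**What to change.** In the Part B vital-signs row of Appendix 6, change the entries for Days 4, 7 and 10 from postdose only to predose and postdose. Take the predose reading during the rest period for the ECG already scheduled then. Section 7.3.3 requires: "Subjects must be supine for at least 5 minutes before blood pressure, pulse rate, and respiratory rate measurements"; Section 7.3.4.1 has the same minimum: "Resting 12-lead ECGs will be recorded after the subject has been supine and at rest for at least 5 minutes". No extra rest period is needed, and Section 7 already places vital signs ahead of blood samples and ECG.

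The cost is three short readings per subject, all while resident, and a fourth procedure at a predose timepoint that already has three. On paper it is one line in the schedule plus the amendment that carries it. Amendment 3, which added a Part A laboratory assessment, was issued as non-substantial and is a close precedent. If the dosing days change after Part A, the predose reading should move with them.
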